7.6 Ethical considerations

This protocol follows the Good Clinical Practices (GCP) and the principles originated in the 18th Medical Assembly of Helsinki, Finland in 1964 and the modifications carried out in Tokyo, Japan in 1975, Venice, Italy in 1983, Hong Kong in 1989, and the 48th General Assembly in Somerset West, South Africa in 1996. 59th General Assembly in Seoul, South Korea, 2008, 64th General Assembly in Fortaleza, Brazil, 2013, where the medical investigation (clinical investigation) was discussed.

Also, the protocol follows the specifications of the General Health Law of Mexico as regards research in the healthcare field, which as per article 17 considers this study, under subsection III, as having a risk higher than the minimum and the administration of drugs. Under said legal framework, the integrity of the individuals, their life, and their safety is respected.

We also follow National Mexican Standard NOM-012-SSA3-2012, which establishes the criteria to carry out investigational projects in the field of human healthcare.

7.6.1 Research Ethics Committee

The main researcher shall submit the study protocol, informed consent, researcher's manual, materials to be handed to the subjects, recruiting materials, and necessary documents to an investigational ethics committee approved by the National Bioethics Commission and currently registered before the Federal Commission for Protection against Sanitary Risks (COFEPRIS), as per local requirements.

The study shall not be initiated in the research center without prior approval of the relevant investigational ethics committees and research committee, compliance with the local regulatory requirements, signing of the confidentiality agreements, economic proposal, and signing of the contracts of each of the main medical researchers.

7.6.1.1 Information for subjects and informed consent form

The informed consent must be obtained before the subject undergoes any procedure indicated in the protocol.

The written consent documents shall incorporate the informed consent elements described in the Declaration of Helsinki and the ICH Good Clinical Practices Guide and shall comply with all applicable laws and regulations.

The main researcher (or a physician who is a member of the site's research team, duly specified by the main researcher as far as delegation of responsibility) shall provide the possible participant with all the information regarding the study characteristics, potential risks, benefits, objectives, and procedures. This information shall be communicated in a language the subject can comprehend, and the subject will be informed that they have the right to interrupt their participation in the study at any time,

without it affecting the relationship with the researcher and/ or their future support. The informed consent shall be given to the possible participant for their consideration, and they must be given enough time to analyze each of the previously mentioned aspects. Should they have any doubts, these must be clarified by the person responsible for obtaining the informed consent. Once the participant agrees to participate in the study, they must sign and date the informed consent letter in the presence of two witnesses that may or may not have a relationship with the study subject, who shall participate during the informed consent process and sign affirming that the process was carried out before any study procedure, that the study information was clearly explained, and that doubts (if any) were clarified.

If a subject is illiterate, their agreement shall be indicated with their fingerprint, and should the subject not be able to grant their adequate written informed consent, a “legally authorized” representative of the subject may provide said consent on behalf of the subject, as per applicable laws and regulations.

The main researcher must also sign and date this consent.

The informed consent must be signed in duplicate by all involved parties and two witnesses. A copy shall be archived in the researcher’s files and another shall be provided to the participant. The researcher must document the date on which the informed consent was signed within the subject’s medical record.

After having obtained the informed consent, a unique identification number shall be assigned to the subject, which will be used during the entirety of the study for the purpose of identification of the participants.

7.6.2 Modifications to the “informed consent”

Any change to the “informed consent” constitutes a modification to this document and must be presented for approval before the Research Ethics Committees and, if applicable, before the competent authorities.

In the modification, a copy of the new version shall be included in the country's language or languages. Said modifications may be implemented only after having obtained written approval of the Research Ethics Committee and having complied with the local regulatory requirements, except for modifications required to eliminate an immediate danger for the study subjects.

Each subject affected by the modification must fill out, date, and sign two original copies of the new version. The subject will receive a signed original copy of the modification and the researcher will keep the second original copy.

7.8 Organization of the center

All individuals to whom the researcher delegates part of the follow-up of the study under their responsibility (co-researcher, sub-researcher, nurse) and any other person participating in this center's study (cardiologist, pharmacist, ...) must appear in the delegation of responsibility form. This document must be submitted at the start of the study and updated if there are changes in any of the individuals participating in the center's study.

8. STUDY DRUG PRODUCT

8.1 Codes, labelling, storage

The dropper bottles shall be issued in their primary and secondary packaging to the various participating research centers, identified with the protocol code, under the specific dosage form and contents in milliliters, as shown in the following image, among others:

8.1.1 Primary packaging

PRO 155	CAUTION: STUDY DRUG FOR RESEARCH PURPOSES ONLY	Subject No. _____
Ophthalmic solution		Initials: _____
Content: 5 mL		ME No.: _____
		Batch: _____
		Cad: _____

8.1.2 Secondary packaging

Drug products No. Batch: Expiration date:	0.09 Protocol: SOPH155-0415/IV Subject No.: _____ Subject initials: _____ Researcher: _____ Ophthalmic route. Give as per the protocol. Storage at room temperature at not more than 30 °C. Do not freeze. Sample for clinical research. Investigational drug product Not for sale. Keep out of reach of children. “Return this container and unused drug products” Laboratorios Sophia S.A. de C.V. [name]. [contact]. Content: 1 bottle	REMOVE LABEL PRO-155 Protocol: SOPH155-0415/IV Drug products No.: _____ Subject initials: _____ Researcher: _____	PRO-155 Protocol: SOPH155-0415/IV Drug products No.: _____ Subject initials: _____ Researcher: _____
---	--	--	--

8.2 Study Drug Product

- The formulation of Zebesten® is composed of the following active agent: Bromfenac 0.09 mg/mL, and inactive agents: povidone, boric acid, sodium borate decahydrate, sodium sulfite, polysorbate 80, disodium edetate dihydrate, benzalkonium chloride, sodium hydroxide, hydrochloric acid, water for injection. It is dispensed in low-density polyethylene dropper bottles for multidose administration as a 5 mL ophthalmic solution. Sanitary record: 108M2014.
- Drug product Lagricel Ofteno® is composed of the following active agent: sodium hyaluronate 0.4 mg (4 mg/mL). It is dispensed in a dropper bottle (with a container closure system that allows to preserve the solution) for unit-dose administration as a 0.5 mL preservative-free ophthalmic solution. Sanitary record: 0208C99 SSA
- Placebo is composed of Zebesten® formulation additives: povidone, boric acid, sodium borate decahydrate, sodium sulfite, polysorbate 80, disodium edetate dihydrate, benzalkonium chloride, sodium hydroxide, hydrochloric acid, water for injection. It is dispensed in low-density polyethylene dropper bottles for multidose administration as a 5 mL ophthalmic solution.

8.3 Study Drug Handling

Previously weighted and packed drug products will be sent from the storage center located at Laboratorios Sophia S.A. de C.V.

The main researcher at the research center is responsible of handling the study drug, including:

- Receipt and storage of the study drug (ME). The receipt of the study drug will be acknowledged by signature and return of the relevant form. The study drug must be kept in a safe area with restricted access. Some special

storage conditions are requested, such as storage at room temperature ≤ 30 °C, do not freeze, and no refrigeration required. The researcher must have a thermohygrometer that records:

- Current temperature
- Minimum temperature
- Maximum temperature
- Percentage of relative humidity

- The main researcher or designated pharmacist must read daily the 4 parameters indicated and record them in the corresponding documentation.

-The expiration date will appear on each box and label.

- The researcher or pharmacist of the research center must use the provided treatment only for subjects participating in the study.

- The study drug must be kept locked and with restricted access throughout the period it remains at the research center.

- Study drug count:

- The researcher and/or pharmacist of the research center and/or a designated team member must fill on real time all the documents provided by the sponsor for the study drug handling.

The study monitor will verify regularly the study drug handling and count.

- At the end of the study, the researcher and study monitor will make a final inventory of the drug products and will record it in the relevant form.

After counting the amount of remaining study drug products returned in every container, the study monitor will pick them for storage and subsequent destruction.

Any defect or deterioration of the study drug or their packaging must be notified to the study monitor. The researcher will notify the monitor all the complaints received from the subjects.

If the study drug is returned to the sponsor before expected (batch withdrawal), the sponsor will prepare an informative letter addressed to the researcher and/or pharmacist of the research center. Local persons responsible of the study will sent this letter to each one of the study centers. When receiving the letter, the researcher and/or pharmacist will identify the subjects that own the treatment when the incident is observed and will contact them immediately. The monitor will organize the return of the study drug to destroy it.

9. STUDY SCHEDULE

Procedure	SCHEDULE (window periods)				
	Baseline visit	Visit 1	Visit 2	Final visit	Follow-up call
	Day 1	Day 7 (± 2)	Day 15 (± 2)	Day 21 (± 2)	Day 36 (± 2)
Eligibility criteria (inclusion and exclusion)	X				
Pregnancy test (if applicable)	X			X	
Informed consent signature	X				
General and ophthalmic medical record	X				
Ocular symptomatology (A, B, C)	X	X	X	X	
OSDI questionnaire	X	X	X	X	
Subject code assignment	X				
Visual capacity	X	X	X	X	
Previous biomicroscopy (D)	X	X	X	X	
Testing of epithelial defects with fluorescein dye	X	X	X	X	
Testing of epithelial defects with lissamine green dye	X	X	X	X	
Breakup time	X	X	X	X	
PIO measurement	X			X	
Posterior ophthalmoscopy under mydriasis	X			X	
Treatment delivery	X				
Start of drug application	X				
End of drug application				X ¹	
Drug return				X	
Subject diary submission	X				
Subject diary review		X	X	X	
Evaluation of adverse events		X	X	X	X
Evaluation of concomitant drug	X	X	X	X	
Follow-up call					X

9.1 Annotations to Activities Schedule:

- A. Burning
- B. Foreign body sensation
- C. Photophobia
- D. Includes testing of conjunctival hyperemia variable

¹ The application ends one day before to fulfill the 20 days indicated in the treatment.

10. DESCRIPTION OF THE PROCEDURES

10.1 General and Ophthalmic Medical Record

It refers to a systems review highlighting the medical and surgical history, indicating the start, evolution and, if applicable, the end of previous conditions.

List the drug products taken and the dates of the last dose; specify their administration route.

A general clinical examination will be performed, including vital signs (blood pressure, body temperature, breaths per minute and heart rate) and anthropometric parameters (weight, size, complexion).

Patients will be asked about previous, chronic or acute ocular conditions, specifying onset or diagnosis time, and their evolution.

If applicable, the optical correction devices used by the subject will be listed, such as frame glasses, contact lenses, magnifying glass, etc. Similarly, the evolution time and use period will be stated.

Then, topical drug products used in eyes and eye adnexa will be investigated. In the case of any systemic drug product directly related to a condition of the eyes or eye adnexa (eyelids, eye socket, lacrimal duct, glands, etc.), it must also be recorded in this section.

Any finding that prevents the protocol procedures from being carried out or the subject from remaining in the study must be recorded. Yes/ No must be indicated in the FRC. In the case of any finding, it must be specified.

It must also be recorded if the subject performs outdoor activities for more than 8 hours (Yes/ No) and if they perform activities in a place with air conditioning for more than 8 hours a day (Yes/ No).

The grade of pterygium must be recorded according to the above classification.

10.2 Pregnancy Test

A urine pregnancy test will be performed in the same facilities of the contracted research center, where the participant of the study will be provided with a home pregnancy test-type device for private use. The subject will be indicated to pour the urine on the absorbing end for 10 seconds, and then to place the included plastic cover and let it stand for 3 minutes on a flat surface with the results window facing upwards. It is important to mention that the device must not be moved during this period.

The result will appear after 3 to 15 minutes. A line will appear in the control window indicating that it is working correctly. Then, a pink line will appear in the results window. Its intensity may vary, but if it appears it indicates that pregnancy is very probable.

The test must be recorded in the FRC, indicating it was performed, the date and results (positive/negative). If the test is not performed, the reason must be specified.

10.3 Ophthalmic Exploration

10.3.1. Visual Capacity Measurement

Basal visual acuity must be tested without using optical correction devices, using a Snellen card in a room with adequate natural or artificial lighting. The result must be documented in the form of a fraction according to the number of lines that the subject was able to read. This information will be reported as visual acuity.

Afterwards, the subject's visual acuity will be tested using the best optical refraction and it will also be recorded in the form of a fraction in the Snellen card. Both values will be reported for statistical purposes (LogMAR). A fraction conversion table is attached to LogMAR.

In the FRC, the result will be recorded as 20 / number for Snellen and as decimal for LogMAR.

- **Visual Examination Standardization**

- At a distance of 3 meters in a well-lit room the research subject will be evaluated as follows:
 - This examination will be performed within the research center
 - The subject will be asked to sit always at the same place and their visual acuity (AV) will be tested using the LogMAR chart. If this chart is not available, the conversion must be performed (Fig. 10.3.1.1). The research subject must keep both eyes open.
 - The research subject must gently cover an eye with the occluder provided by Laboratorios Sophia S.A. de C.V., (all the research subjects must use the same occluder to cover their eye) while they read aloud the smallest line of letters they are able to see. This examination is performed in each eye, one at a time, starting with the right eye (OD).
 - The physician must point to the line the research subject must read.
 - The same steps are applied for the visual capacity test.

[figure not shown]
LogMAR	VAR	Snellen (m)	Decimal Snellen	Snellen (ft)
1.0	50	6/60	0.10	20/200
0.9	55	-	-	20/150
0.8	60	6/36	0.15	20/120
0.7	65	-	0.20	20/100
0.6	70	6/24	-	20/80
0.5	75	6/18	0.30	20/60
0.4	80	-	0.40	20/50
0.3	85	6/12	0.50	20/40
0.2	90	6/9	-	20/30
0.1	95	-	0.75	20/25
0.0	100	6/6	1.00	20/20
-0.1	105	6/5	-	20/15
-0.2	110	6/4	1.50	-
-0.3	115	6/3	2.00	20/10

Fig. No. 10.3.1.1. LogMAR conversion table

[figure not shown]

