13.2 Security evaluation

The security variables of the use of Zebesten ® will be evaluated in the appointed visits in the chronogram, by means of the following parameters.

1. Tear film breakup time
2. Visual capacity
3. Intraocular pressure
4. Epithelial defects
5. Adverse events.

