13.3 Efficacy assessment

The efficacy variables of Zebesten® use will be evaluated in the appointed visits in the chronogram, by means of the following parameters:

1. Conjunctival hyperemia
2. OSDI score

Table of scales and variables measurement method

Variable	Unit	Symbol	Type	Measurement method	Normal value
Age	Years	--	Continuous	Calculated as of the date of birth	NA
Gender	Female Male	F/M	Nominal	Direct questioning	NA
Pterygium	Grade 0 Grade I Grade II Grade III Grade IV	--	Ordinal	Direct observation	Grade 0
Adverse events	Number of cases	N	Discreet	Counting	NA
Intraocular pressure	Mercury millimeters	MmHg	Continuous	Goldman applanation tonometry	11-21
Visual capacity	Fraction	Snellen	Nominal	Card	
Tear film breakup time	Seconds	s	Continuous	Direct counting	> 10
OSDI questionnaire	Points	--	Discreet	Questionnaire	
epithelial defects	Grade I Grade II Grade III Grade IV Grade V	--	Discreet	Direct observation with fluorescent staining and lissamine green	Oxford scale

Signs and ophthalmologic symptoms					
conjunctival hyperemia	Very mild Mild Moderate Severe	--	Ordinal	Direct observation. Efron classification.	Normal
burning	Present absent	--	Nominal	Direct questioning	Absent
Foreign body sensation	Present Absent	--	Nominal	Direct questioning	Absent
Photophobia	Present Absent	--	Nominal	Direct questioning	Absent
Prior segment	Normal Abnormal	--	Nominal	Direct observation	Normal

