14. PROPOSED STATISTICAL ANALYSIS

The statistical analysis will be performed by a researcher blinded to the intervention groups.

The continuous quantitative variables will be expressed and presented via measures of central tendencies and of dispersion (media, standard deviation and ranges).

The nominal qualitative variables and ordinals will be presented via frequencies and proportions.

The Kolmogorov-Smirnov test will be performed in order to know the normal distribution or not of the obtained results in each study group. Also, the Levene test will be performed in order to know if the variables are the same or different.

Assuming a normal distribution of the data, the intra-group differences will be determined via the t test for paired samples, in the case of the quantitative variables. For the quantitative variables the χ^2 test (chi squared) will be used and in case that the expected frequencies are less than 5 the exact Fisher test will be used.

The differences among the groups will be analyzed via the t test in case of quantitative variables. For the quantitative variables tables of contingency 2x2 will be made and the differences will be calculated via χ^2 (chi squared) with Yates correction in case that the expected frequencies are less than 5 the exact Fisher test will be used).

The level of significance will be alpha of 0.05 or less.

A final statistical analysis will be included to all the subjects that complete 3 visits in the chronogram of activities.

15. Results report

The results obtained during the development of the investigation's protocol will be the responsibility of the sponsor, who is under obligation of reporting them to the pertinent authorities. Plus each one of the participating researchers will receive a results report.

The objective is to achieve the publication of the study on an international magazine with the objective of disseminate the scientific knowledge obtained.

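### Section 10.3.1 puts visual capacity on the LogMAR scale for statistics, section 13.3 types it as a nominal Snellen fraction, and section 14 does not settle which governs

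*Combined protocol and SAP*

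**What the plan says.** **Section 10.3.1 (measurement).** Acuity is tested without correction and then with best refraction. On both results: "Both values will be reported for statistical purposes (LogMAR"). On the case report form, "the result will be recorded as 20 / number for Snellen and as decimal for LogMAR". A LogMAR chart is to be used; "If this chart is not available, the conversion must be performed (Fig. 10.3.1.1"). That figure is a 14-step table from 1.0 to -0.3 in steps of 0.1.

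**Section 13.2 (safety).** Visual capacity is item 2 of the five safety parameters. The Summary and section 13 also list it as a secondary outcome.

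**Section 13.3 (table of scales).** The entry reads "Visual capacity Fraction Snellen Nominal". The same table types intraocular pressure and tear film breakup time as continuous and conjunctival hyperemia as ordinal.

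**Section 14 (analysis).** Methods follow type. "The continuous quantitative variables will be expressed and presented via measures of central tendencies and of dispersion", and "The nominal qualitative variables and ordinals will be presented via frequencies and proportions". Between arms there are two rules: a t test, and 2x2 contingency tables with Yates-corrected chi-squared or Fisher's test. As printed, both rules are for quantitative variables. Neither visual capacity nor LogMAR is mentioned.

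**The concern.** Section 13.3 has the only table that gives each variable a statistical type, and section 14 works from type alone. An analyst who follows those two sections literally would handle acuity as gender is handled: as unordered categories. Gaining a line and losing a line would then be merely different categories. A 2x2 table would also need acuity to be split in two, and no cut-point is given, so the split could be chosen after the data are seen.

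For a safety variable the costly error is a false finding of no difference. An order-blind comparison makes that error more likely when one arm has lost vision. An analyst who follows section 10.3.1 would do something quite different. The plan should not leave that choice open.

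**Working it through.** **1. The two routes side by side**

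| | Section 10.3.1 followed | Section 13.3 followed |
|---|---|---|
| Scale | LogMAR decimal | Snellen fraction, nominal |
| Summary under section 14 | Mean, SD, range | Frequencies and proportions |
| Between-arm test under section 14 | t test | 2x2 chi-squared or Fisher (inferred) |
| Cut-point needed | No | Yes; none stated |

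The inferred cell depends on reading the second mention of quantitative variables in section 14 as qualitative. As printed, the two between-arm rules cover the same class, and that reading is the one under which they differ. It is likely, but it is not what the text says.

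**2. What the choice could cost**

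The documents give no mean, SD, effect size or power for visual capacity, so there is no figure to reproduce. The following is illustration only.

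- From the plan: 69 evaluable eyes per arm (section 12.4, before the allowance for losses), 0.1 LogMAR steps (section 10.3.1), alpha 0.05 (section 14, taken as two-sided).
- Assumed: normal acuity rounded to the nearest step, eyes independent, one time point, and a worsening of 0.5 SD in one arm.

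Simulated power, 3,000 trials per setting:

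| Mean, SD, shift (LogMAR) | t test on LogMAR | Chi-squared over all levels, order ignored |
|---|---|---|
| 0.10, 0.12, 0.06 | 81% | 46% |
| 0.10, 0.15, 0.075 | 82% | 41% |
| 0.15, 0.20, 0.10 | 82% | 36% |

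Across repeated runs the ranges are 81-82% and 35-46%. The t-test figure follows largely from the assumed shift: 0.5 × √(69/2) = 2.94, and Φ(2.94 − 1.96) ≈ 84% before the small loss from rounding. The informative part is the gap between the columns.

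A second set of assumptions (mean 0.2, a one-line mean loss of 0.1, 69 per arm) gives t test against unordered chi-squared of 97% vs 71% at SD 0.15, 83% vs 35% at SD 0.20, and 46% vs 12% at SD 0.30. The size of the gap moves with the assumptions; its direction does not.

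**3. The missing cut-point**

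In the first set of settings, a 2x2 split at 20/40 or better gives 6-47% power, and a split at 20/25 or better about 55-58%. Neither split is proposed in the documents. In the protocol's table 20/20 is 0.0 and 20/40 is 0.3, so a three-line fall between them does not register at a split of 20/40 or better.

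**4. Which rule to use for counting lines lost**

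Computing LogMAR as log10(denominator/20) and counting losses of 0.2 or more does not agree with the protocol's table. Of the 11 two-line steps with a foot-Snellen value at both ends:

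- log10(1.5) = 0.176: 20/10 to 20/15, 20/20 to 20/30, 20/40 to 20/60, 20/80 to 20/120, 20/100 to 20/150 (five steps)
- log10(1.6) = 0.204: 20/25 to 20/40, 20/50 to 20/80 (two steps)
- log10(1.667) = 0.222: 20/15 to 20/25, 20/30 to 20/50, 20/60 to 20/100, 20/120 to 20/200 (four steps)

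Five of the 11 would be missed, although the table makes each of them exactly 0.2. Counting in steps of the table avoids this.

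**The case against.** The strongest reply is that section 10.3.1 is the one place that says how acuity is to be used statistically, and it says LogMAR. It supplies a conversion table and puts the LogMAR decimal on the case report form. On that view the word nominal in section 13.3 is a slip, section 14 applies a t test, and no power is lost. This largely stands. A reader might infer that the plan has settled on a nominal analysis that will hide visual loss; the documents do not support that. They do leave the conflict open. Section 10.3.1 is a measurement procedure that names no summary or test, and section 14 selects by type, for which the only entry is nominal.

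Two further points are fair. The chi-squared route is an inference from a faulty sentence; what section 14 states outright for nominal variables is only that they are presented as frequencies. And the power figures rest on assumed values, on independent eyes although section 7.2 admits both eyes of a subject, and on an all-levels chi-squared test that section 14 does not name for comparing arms. They show what is at stake, not how this plan will perform.

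There are also other safeguards. Acuity is measured at four visits, any unfavourable sign or symptom is an adverse event under section 17.1.1, and adverse events are a primary outcome. A frequency table by arm would still show the direction of a shift to someone who looked. These reduce the risk that loss in an individual goes unnoticed. They do not supply the between-arm analysis of visual capacity.

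**Conclusion.** The point holds as an unreconciled contradiction. Section 10.3.1 and the section 13.3 table assign different scales to one of the five safety variables, and section 14 does not say which applies. If the table is followed, the order of acuity is discarded and the ability to detect a loss of vision falls: in the illustration, from about 81-82% to 35-46%, under assumed means, SDs and a 0.5 SD worsening in 69 independent eyes per arm. If section 10.3.1 is followed, that loss does not arise.

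Two gaps remain on either route: the plan does not say whether the uncorrected or the best-corrected value is analysed, and it makes no use of the Day 1 value when comparing arms. The matter should be corrected, but it concerns a secondary safety variable with no powered hypothesis and does not touch the primary efficacy comparison.

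**What to change.** 1. In the section 13.3 table, change the visual capacity entry from a nominal Snellen fraction to LogMAR, continuous, to agree with section 10.3.1.
2. In section 14, name visual capacity, compare the arms on LogMAR adjusted for the Day 1 value, and state whether the best-corrected or the uncorrected value is analysed.
3. In section 14, add a table by arm of eyes losing two or more lines from Day 1, counted in steps of Fig. 10.3.1.1. Use one conversion rule at all centres, and do not use log10(denominator/20) with a 0.2 cut-off. Fig. 10.3.1.1 has no foot-Snellen value at LogMAR -0.2 and no 20/70 line, so the rule should say how readings off the table are assigned.
4. In section 14, correct the repeated reference to quantitative variables so that the class receiving contingency tables is clear.

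The cost is one table cell and a few sentences. Acuity is already measured on Day 1 and at every later visit, and LogMAR is already on the case report form, so no procedure or data collection changes.
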